8.1.3. Population of Interest

The primary pharmacokinetic analyses will be based on the "Pharmacokinetic" population, unless otherwise specified.

8.1.4. Strategy for Intercurrent (Post-Randomization) Events

- Study completion (i.e. as specified in the protocol) was defined as completing all phases of the study including the follow-up visit.
- Withdrawn participants may be replaced in the study. Replacement participants, enrolled will be dosed with the next planned treatment of the withdrawn participant, and they will not receive any treatment that the withdrawn participant has already received with the exception of the need to increase participants numbers to obtain the minimum number of evaluable participants required for interim decisions, and to obtain data in any other treatment that is required for a valid comparison. Replacement participants will receive the required treatments in the same order as planned for the original participant.
- All available data from participants who were withdrawn from the study will be listed and all available planned data will be included in summary tables and figures, unless otherwise specified.

8.2. Secondary Pharmacokinetic Analyses

8.2.1. Endpoint / Variables

8.2.1.1. Drug Concentration Measures

Refer to Appendix 5: Data Display Standards & Handling Conventions (Section 10.5.3 Reporting Standards for Pharmacokinetic).

• Descriptive statistics (n, arithmetic mean, standard deviation, standard error, 95% CI, minimum, median and maximum) of circulating glucuronide metabolite (M8; GSK3562183) and des-methyl metabolite (M9; GSK2997852) will be investigated in healthy participants after single-day and repeat dosing of GSK2982772

9. **REFERENCES**

• PKOne and relevant information on Standards for the Transfer and Reporting of PK Data using HARP available within IDSL standards.

10. APPENDICES

10.1. Appendix 1: Protocol Deviation Management

- Protocol deviations will be tracked by the study team throughout the conduct of the study in accordance with the Protocol Deviation Management Plan.
 - Data will be reviewed prior to freezing the database to ensure all important deviations are captured and categorised on the protocol deviations dataset.
 - This dataset will be the basis for the summaries and listings of protocol deviations.

10.2. Appendix 2: Schedule of Activities

10.2.1. Protocol Defined Schedule of Events

10.2.1.1. Part A (Cohort 1)

	Screening	St	tudy F	Period	l (Day	/s)	Follow-Up	
Procedure	(Up to 28 days						(No more than 14	Notes
	before Day	-1	1	2	3	4	days post	
	1)						last dose)	
Outpatient Visit	Х						Х	
Admission to Clinical Unit		Х						
Inpatient Stay at Clinical Unit			\leftarrow	==X==	=→			
Discharge from Clinical Unit						Х		Following completion of all assessments.
Informed Consent	Х							
Inclusion and Exclusion Criteria	Х							
Demography	Х							
Full Physical Examination	х							Additional exams/screens may be performed, or brief exams made full exams, by the Investigator, as deemed necessary (e.g. where safety or laboratory findings indicate). Tests will be conducted within site specified standards.
Brief Physical Examination		Х		Х		Х		resis will be conducted within site specified standards.
Height	Х							
Weight	Х							
Drug/Alcohol/Smoking Screen	Х	Х						Tests include alcohol breath test, smoking breath test and urine drug screen.
Medical/Medication/Drug/Alcohol History	х							
HIV, Hepatitis B and C Screening	Х							
Tuberculosis Test	Х							Conducted at the standard practice of the site.
Serum Pregnancy Test (WOCBP only)	Х						Х	
Urine Pregnancy Test (WOCBP only)		Х				Х		
Highly effective contraceptive method (WOCBP only)	Х	Х	Х	Х	Х	Х	Х	Must use method for a minimum of 28 days prior to first dose of study medication until the follow-up visit

	Screening	St	udy F	Period	l (Day	/s)	Follow-Up	
Procedure	(Up to 28 days before Day 1)	-1	1	2	3	4	(No more than 14 days post last dose)	Notes
Contraception with male condoms (WOCBP using hormonal contraceptive method and male subjects with female partners of childbearing potential only)		х	х	Х	х	х	Х	
Meals		х	Xa	х	х	х		 ^a On Day 1, subjects will fast 8hr overnight prior to dose 1. A breakfast will be served approximately 2hr after dose 1. TID dosing: On Day 1, lunch and dinner will be served between 2 to 3hr prior to doses 2 and 3, respectively. BID dosing: On Day 1, lunch will be served approximately 4 to 5hr after dose 1. Dinner will be served between 2 to 3hr prior to dose 2. A snack may be consumed approximately 2 to 3hr after dose 2. Water is permitted with dosing and at all times. Subjects will receive standardized meals scheduled at the same time in each period.
Haem/Chem/Urinalysis Test (Include Liver Chemistries)	х	Х	Х	Х		Х	Х	Non-fasted samples can be collected on Day -1 and Follow-Up Visit.
PK Blood Sampling			x	Х				TID Dosing: PK samples to be taken pre-dose on Day 1 and then at the following time points post first-dose: 20min, 40min, 1hr, 1hr 30min, 2hr, 3hr, 5hr, 7hr, 7hr 20min, 7hr 40 min, 8hr, 8hr 30min, 9hr, 10hr, 12hr, 14hr, 14hr 20min, 14hr 40 min, 15hr, 15hr 30min, 16hr, 17hr, 19hr, 22hr, 24hr. BID Dosing: PK samples to be taken pre-dose on Day 1 and then at the following time points post first-dose: 20min, 40min, 1hr, 1hr 30min, 2hr, 3hr, 4hr, 6hr, 8hr, 10hr, 12hr, 12hr 20min, 12hr 40min, 13hr, 13hr 30min, 14hr, 15hr, 16hr, 19hr, 22hr, 24hr. Remaining PK plasma samples from Part A may be analysed for metabolite sampling.
Neuro. Examination			< →	X	÷۷	<→		TID Dosing: Neurological examinations to be conducted either on Day -1 or pre-dose Day 1 and then at the subsequent time points post first-dose on Day 1: 2hr, 9hr, 16hr, 24hr and 48hr. Then 24 and 48hr after the last dose administered on Day 1. BID Dosing: Neurological examinations to be conducted either on Day -1 or pre-dose Day 1 and then at the subsequent time points post first-dose: 2hr, 14hr, 24hr and 48hr. Then 24 and 48 hr after the last dose administered on Day 1. Continuous at least 24hr post-evening dose. Initiate at least 15 min. prior to dosing.

	Screening	St	tudy F	Period	d (Day	/S)	Follow-Up	
Procedure	(Up to 28 days before Day 1)	-1	1	2	3	4	(No more than 14 days post last dose)	Notes
12-Lead ECG	Х	Х	Т	х	÷	×→		Vital signs to include HR, BP, temperature and respiration rate. TID Dosing: 12-Lead ECG and Vital Signs to be conducted on Day -1 and pre-dose on
Vital Signs	x	х	Т	x	÷	×→	х	Day 1 and then at the subsequent time points post first-dose: 40min, 2hr, 4hr, 7hr (pre- 2^{nd} dose), 9hr, 14hr (pre- 3^{rd} dose), 16hr, 24hr and 48hr. Then 24 and 48hr after the last dose administered on Day 1. BID Dosing: 12-Lead ECG and Vital Signs to be conducted on Day -1 and pre-dose on Day 1 and then at the subsequent time points post first-dose: 40 min, 2hr, 4hr, pre- 2^{nd} dose, 12hr 20 min, 14hr, 24hr and 48 hr. Then 24 and 48hr after the last dose administered on Day 1. T = Triplicate.
Randomization		2	X					Randomization can occur on either Day -1 or Day 1.
Study Treatment			Xp					^b TID dosing : GSK2982772 or placebo will be administered using a 7hr, 7hr dosing interval. BID dosing : GSK2982772 or placebo will be administered using a 12hr dosing interval.
Pharmacogenetic Sample (PGx)			x					A PGx blood sample is collected at the Day 1 visit, after the subject has been randomized and provided informed consent for genetic research. If the sample is not collected at the Day 1 visit, it can be collected at any time during the study after randomization.
AE Review		\leftarrow	=====	==X=	====	=→	Х	
SAE Review		-		:==X=		-	Х	
Concomitant Medication Review	Х	\leftarrow		:==X=	====	=→	Х	

10.2.1.2. Part B (Cohorts 2-5)

Procedure	Screening (Up to 28 days before Day 1)								Stu	dy Pe	riod (Days)								Follow- up (No more than 14 days post last dose)	Notes
		- 1	1	2	3	4	5	6	7	8	9	10	11	12	13	14	15	16	17		
Outpatient Visit	Х																			Х	
Admission to Clinical Unit		Х																			
Inpatient Stay at Clinical Unit			←=	=====	=====	====	====:	=====	====:	=====	X===	====:	=====	====	====:		====:	==→			
Discharge from Clinical Unit																			x		Following completion of all assessments.
Informed Consent	Х																				
Inclusion and Exclusion Criteria	Х																				
Demography	Х																				
Full Physical Examination	Х																		Х		Additional exams/screens
Brief Physical Examination		х		х		Х			Х			Х					х			Х	may be performed, or brief exams made full exams, by the

205184

205184

Procedure	Screening (Up to 28 days before Day 1)								Stu	dy Pe	riod (Days)								Follow- up (No more than 14 days post last dose)	Notes
		- 1	1	2	3	4	5	6	7	8	9	10	11	12	13	14	15	16	17		
																					Investigator, as deemed necessary (e.g. where safety or laboratory findings indicate). Tests will be conducted within site specified standards.
Height	Х																		X		
Weight Drug/Alcohol/Smoking Screen	X	х							X										X		Tests include alcohol breath test, smoking breath test and urine drug screen.
Medical/Medication/ Drug/Alcohol History	Х																				
HIV, Hepatitis B and C Screening	Х																				

Procedure	Screening (Up to 28 days before Day 1)								Stu	dy Pe	riod (Days)								Follow- up (No more than 14 days post last dose)	Notes
		- 1	1	2	3	4	5	6	7	8	9	10	11	12	13	14	15	16	17		
Tuberculosis Test	Х																				
Anti-Nuclear Antibody	Х								Х										Х		
Serum Pregnancy Test (WOCBP only)	Х																			Х	
Urine Pregnancy Test (WOCBP only)		Х																	Х		
Highly effective contraceptive method (WOCBP only)	Х	x	x	х	х	х	x	x	X	х	х	x	х	х	х	х	х	Х	х	Х	Must use method for a minimum of 28 days prior to first dose of study medication until the follow- up visit.
Contraception with male condoms (WOCBP using hormonal contraceptive method and male subjects with female partners of childbearing potential only)		x	X	х	х	х	x	X	X	Х	х	X	Х	х	x	х	Х	Х	x	Х	
C-SSRS	Х	÷	X>						Х										Х	Xc	May be

Procedure	Screening (Up to 28 days before Day 1)								Stu	dy Pe	riod (Days)								Follow- up (No more than 14 days post last dose)	Notes
		- 1	1	2	3	4	5	6	7	8	9	10	11	12	13	14	15	16	17		
																					completed on either Day -1 or Day 1, but no later than 1hr prior to dosing. To be completed pre- dose on Day 7. ° C-SSRS to be conducted on follow-up only in the instance that a subject withdraws from the study.
Meals		x	Х	х	Х	Х	Х	Х	Х	Х	Х	Х	Х	х	х	X	х	Х	x		TID Dosing: On Day 1 through 14 subjects will fast 8hr overnight. Breakfast will be served approximately

Procedure	Screening (Up to 28 days before Day 1)								Stu	dy Pe	riod (Days)								Follow- up (No more than 14 days post last dose)	Notes
		- 1	1	2	3	4	5	6	7	8	9	10	11	12	13	14	15	16	17		
																					2hr after dosing on Days 1-8, 10, 12 and 13 and 2hr after dosing on Day 14. A "standard" and a "high fat" breakfast will be served approximately 30 minutes prior to dosing on Day 9 and Day 11, respectively. On all study days, lunch and dinner will be served between 2 to 3hr prior to dose 2 and

205184

dose 3,

g								Stu	dy Pe	riod (Days)								Follow- up (No more than 14 days post last dose)	Notes
	- 1	1	2	3	4	5	6	7	8	9	10	11	12	13	14	15	16	17		
																				respectively. BID Dosing: On Day 1 through 14, subjects will fast 8hr overnight prior to dose 1. A breakfast will be served

Procedure	Screening (Up to 28 days before Day 1)								Stu	dy Pe	riod (Days)								(No more than 14 days post last dose)	Notes
		- 1	1	2	3	4	5	6	7	8	9	10	11	12	13	14	15	16	17		
																					respectively. BID Dosing: On Day 1 through 14, subjects will fast 8hr overnight prior to dose 1. A breakfast will be served approximately 2hr after dose 1. Lunch will be served approximately 4-5hr after dose 1. Dinner will be served between 2-3hr prior to dose 2. A snack may be consumed approximately 2-3hr after dose 2.

Procedure	Screening (Up to 28 days before Day 1)								Stu	dy Pe	riod (Days)								Follow- up (No more than 14 days post last dose)	Notes
		- 1	1	2	3	4	5	6	7	8	9	10	11	12	13	14	15	16	17		
																					Water is permitted with dosing and at all times. Subjects will receive standardized meals scheduled at the same time in each period. Meals will be served as per the site schedule on Days -1, 16 and 17.
Haem/Chem/ Urinalysis Test (Include Liver Chemistries)	Х	x	x	x		x			x			x					x			х	Collection on Day 1 no later than 1hr prior to dosing. To be drawn pre- dose on Days 2, 4, 7 and 10.
Fasting lipid panel	Х		Х	Х		Х			Х			Х					Х			Х	Collection on

Procedure	Screening (Up to 28 days before Day 1)								Stu	dy Pe	riod (Days)								Follow- up (No more than 14 days post last dose)	Notes
		- 1	1	2	3	4	5	6	7	8	9	10	11	12	13	14	15	16	17		
																					Day 1 no later than 1hr prior to dosing. To be drawn pre- dose on Days 2, 4, 7 and 10.
Holter Monitoring (24- hour)	Х																				
Telemetry			>	()	<										>	<				Continuous at least 24 hr post-evening dose. Initiate at least 15 min. prior to dosing.
PK blood sampling			Xq	Xe	Xe	Xe	Xe		Xe		Xţ		Xţ			Xa					^d On Day 1, PK samples will be collected pre-dose and at the following time points post first-dose: 20min, 40min, 1hr, 1hr 30min, 2hr, 3hr, 5hr,

Procedure

Screening (Up to 28 days before Day 1)								Stu	dy Pe	riod (Days)								Follow- up (No more than 14 days post last dose)	Notes
	- 1	1	2	3	4	5	6	7	8	9	10	11	12	13	14	15	16	17		
																				7hr, 9hr and 11hr. • On Days 2,3 4, 5 and 7 pre- dose samples only. f Days 9, and 11: Cohort 2, 3 and Cohort 4 PK sampling will be collected pre- dose and at the following time points post first-dose: 20min, 40min, 1hr, 1hr 30min, 2hr, 3hr, 5hr, 7hr (prior to 2 nd dose) 7hr 20min, 7hr 40 min, 8hr, 8hr 30min, 9hr, 10hr, 12hr.

205184

Study Period (Days)		 		Follow- up (No more than 14 days post last dose)	Notes

Procedure	Screening (Up to 28 days before Day 1)		Study Period (Days)															more than 14 days post last dose)	Notes		
		- 1	1	2	3	4	5	6	7	8	9	10	11	12	13	14	15	16	17		
																					Cohort 5 is currently not planned to have PK assessment but may be included depending on outcome of food effect in Cohorts 2, 3 and 4. ^g Day 14 sampling for Cohorts 2, 3, 4 and 5 will be over 24hr according to the following schedules: For TID Dosing: PK samples to be taken pre-dose and then at the

Procedure	Screening (Up to 28 days before Day 1)		Study Period (Days)														Follow- up (No more than 14 days post last dose)	Notes			
		- 1	1	2	3	4	5	6	7	8	9	10	11	12	13	14	15	16	17		
																					following time points post first-dose: 20min, 40min, 1hr, 1hr 30min, 2hr, 3hr, 5hr, 7hr (pre-2 nd dose) 7hr 20min, 7hr 40 min, 8hr, 8hr 30min, 9hr, 10hr, 12hr, 14hr (pre 3 rd dose), 14hr 20min, 14hr 40 min, 15hr, 15hr 30min, 16hr, 17hr, 19hr, 22hr, 24hr. For BID Dosing: PK samples to be taken pre-dose on Day 1 and then at the

Procedure	ocedure Screening (Up to 28 days before Day 1)															Follow- up (No more than 14 days post last dose)	Notes				
		- 1	1	2	3	4	5	6	7	8	9	10	11	12	13	14	15	16	17		
																					subsequent time points post first-dose: 20min, 40min, 1hr, 1hr 30min, 2hr, 3hr, 4hr, 6hr, 8hr, 10hr, 12hr (pre 2 nd dose), 12hr 20min, 12hr 40min, 13hr, 13hr 30min, 14hr, 15hr, 16hr, 19hr, 22hr, 24hr.
Metabolite sampling																X ^h					^h Metabolite sampling will be conducted pre-dose and 2hr post first dose on Day 14 only.
4β-hydroxycholesterol sampling			Xi														Xi				ⁱ Sample to be taken pre-dose on Day 1 in a

Procedure	Screening (Up to 28 days before Day 1)								Stu	dy Pe	riod (Days)								Follow- up (No more than 14 days post last dose)	Notes
		- 1	1	2	3	4	5	6	7	8	9	10	11	12	13	14	15	16	17		
																					fasted state. ^j Sample to be taken at 24hr post first dose on Day 14. Sample should be in a fasted state.
Neuro. examination			x	x	x				x									X			TID Dosing: Neurological examinations to be conducted either on Day- 1 or pre-dose Day 1 and then at the subsequent time points post first dose: 2hr, 9hr, 16hr, 24hr and 48hr. To be completed pre-

205184

completed pre-dose on Day 7

Procedure	ocedure Screening (Up to 28 days before Day 1)															Follow- up (No more than 14 days post last dose)	Notes				
		- 1	1	2	3	4	5	6	7	8	9	10	11	12	13	14	15	16	17		
			1																		and then 48 hr post-last dose on Day 14. BID Dosing: Neurological examinations to be conducted pre- dose either on Day-1 or Day 1 and then at the subsequent time points post first dose: 2hr, 14hr, 24hr and 48hr. To be completed pre-dose on Day 7 and then 48hr post- last dose on Day 14.
12-Lead ECG	Х	Х	Т	Х		Х			Х							Х				Х	Vital signs to include HR,
Vital signs	Х	Х	Т	Х	Х	Х	Х	Х	Х	Х	Х	Х	Х	Х	Х	Х	Х	Х	Х	Х	Include HR, BP,

Procedure	Screening (Up to 28 days before Day 1)								Stu	dy Pe	riod (Days)								Follow- up (No more than 14 days post last dose)	Notes
		- 1	1	2	3	4	5	6	7	8	9	10	11	12	13	14	15	16	17		
																					temperature and respiration rate. On Day 1: TID Dosing: 12-Lead ECG and Vital Signs to be conducted on Day-1 and pre- dose Day 1 and then at the subsequent time points post first-dose: 40min, 2hr, 4hr, 7hr (pre- 2 nd dose), 9hr, 14hr (pre-3 rd dose), 16hr, 24hr, 48hr. Then 24 and 48hr after the first dose and last dose

Procedure	Screening (Up to 28 days before Day 1)								Stu	dy Pe	riod (Days)								Follow- up (No more than 14 days post last dose)	Notes
		- 1	1	2	3	4	5	6	7	8	9	10	11	12	13	14	15	16	17		
																					administered on Day 14. BID Dosing: 12-Lead ECG and Vital Signs to be conducted pre- dose either on Day-1 or Day 1 and then at the subsequent time points post first-dose: 40 min, 2hr, 4hr, 12hr (pre- 2 nd dose), 14hr, 24hr, 48hr. Then 24 and 48hr after the first and last dose administered on Day 14. On Days 3 to 14, pre-dose

Procedure	Screening (Up to 28 days before Day 1)								Stu	dy Pe	riod (Days)								Follow- up (No more than 14 days post last dose)	Notes
		- 1	1	2	3	4	5	6	7	8	9	10	11	12	13	14	15	16	17		
																					samples only. T = Triplicate.
Randomization			Х																		Randomization can occur on either Day -1 or Day 1.
Study Treatment			×	х	x	×	х	x	×	×	×	×	×	х	×	×					TID dosing: GSK2982772 or placebo will be administered using a 7hr, 7hr and 10hr dosing interval. BID dosing: GSK2982772 or placebo will be administered using a 12hr dosing interval.
Pharmacogenetic Sample (PGx)			Х																		A PGx blood sample is collected at the Day 1 visit,

Procedure	Screening (Up to 28 days before Day 1)								Stu	dy Pe	riod (Days)								Follow- up (No more than 14 days post last dose)	Notes
		- 1	1	2	3	4	5	6	7	8	9	10	11	12	13	14	15	16	17		
																					after the subject has been randomized and provided informed consent for genetic research. If the sample is not collected on Day 1, it can be collected at any time during the study after randomization.
AE review		Х	Х	Х	Х	Х	Х	Х	Х	Х	Х	Х	Х	Х	Х	Х	Х	Х	Х	Х	
SAE review		Х	Х	Х	Х	Х	Х	Х	Х	Х	Х	Х	Х	Х	Х	Х	Х	Х	Х	Х	
Concomitant medication review	Х	х	Х	Х	Х	Х	Х	Х	Х	Х	Х	Х	Х	Х	Х	Х	Х	Х	Х	Х	

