2. SCHEDULE OF ACTIVITIES (SOA)

Protocol waivers or exemptions are not allowed with the exception of immediate safety concerns. Therefore, adherence to the study design requirements, including those specified in the Schedule of Activities (SoA) tables (Section 2.1 and Section 2.2), are essential and required for study conduct.

Supplementary study conduct information not mandated to be present in this protocol is provided in the Study Reference Manual (SRM). The SRM will provide the site personnel with administrative and detailed technical information that does not impact subject safety.

This section lists the procedures and parameters of each planned study assessment. The exact timing of each assessment is listed in the SoA tables (Section 2.1 and Section 2.2).

The following points must be noted:

- If assessments are scheduled for the same nominal time, THEN the assessments should occur in the following order:
 1. 12-Lead ECG
 2. Vital Signs
 3. Blood Draws

Note: The timing of the assessments should allow the blood draw to occur at the exact nominal time.

- The timing and number of planned study assessments, including safety, pharmacokinetic, or other assessments may be altered during the course of the study based on newly available data (e.g. to obtain data closer to the time of peak plasma concentrations) to ensure appropriate monitoring.
- The change in timing or addition of time points for any planned study assessments must be documented in a Note to File, which is approved by the relevant GSK study team member and then archived in the study sponsor and site study files, but this will not constitute a protocol amendment.
- No more than 500 mL of blood will be collected over the duration of the study, including any extra assessments that may be required.
- The Institutional Review Board/Independent Ethics Committee (IRB/IEC) will be informed of any safety issues that require alteration of the safety monitoring scheme or amendment of the Informed Consent Form.

A table defining the allowed variance in timings of assessments without being considered a protocol deviation will be included in the SRM.

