5.7. Dose Justification

An adaptive dose-escalation approach, guided by the observed safety, tolerability and plasma PK exposure will be taken to allow an efficient evaluation of a range of doses above the 120 mg BID dose that was evaluated in the FTiH study.

The initial starting dose planned is 120 mg TID and the maximum daily dose is anticipated to be approximately 720 mg administered as 240 mg TID and 360 mg BID.

For doses of up to 120 mg BID, the pharmacokinetics of GSK2982772 are approximately linear. Please see GSK2982772 IB [GlaxoSmithKline Document Number [2014N204126_02](#)]. After attainment of C_{max} , at approximately 2 hours post-dose, GSK2982772 concentrations decline rapidly until about 12 hours post-dose, with a $t_{1/2}$ of approximately 2 to 3 hours. The majority of the systemic exposure to GSK2982772 is observed within the first 12 hours after administration. Following repeat dosing of GSK2982772, there is no evidence of drug accumulation for either a QD or BID dosing regimen. The major circulating metabolite is an N-glucuronide which accounts for approximately 70% of drug related material in plasma. Since glucuronidation is a high

capacity clearance mechanism it is unlikely that the kinetics of GSK2982772 will become saturable with more frequent dosing nor at the higher doses planned in the current study.

Due to the short half-life of GSK2982772 (~2-3 hr), it is expected that steady-state will be achieved by Day 2 of dosing and that negligible accumulation will be observed. Therefore, the PK safety margins described for Day 1 and for Day 14 of dosing will be similar.

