10.5. Dose Escalation Committee

The decision to proceed to the next dose level of GSK2982772 in each Cohort will be made by a DEC consisting of the Principal Investigator (or appropriate designee), Medical Monitor, GSK Clinical Investigational lead and/or Study Team Leader, GSK Pharmacokineticist, a GSK GCSP representative and GSK Statistician. All GSK personnel including the GSK Statistician and the GSK Pharmacokineticist will remain unblinded throughout the course of the study.

For Part A, dose escalation decisions will be based on data obtained from 6 or more subjects receiving GSK2982772 at the prior dose level. The review of the data set will consist at a minimum of: listings of all AEs, clinical laboratory results, flagged vital signs, flagged findings during continuous cardiac monitoring (telemetry), ECG and PK results derived from 24-hour plasma profiles.

The decision and selection of dose to proceed to Part B, will be made by the DEC based on safety, tolerability, and PK data from the same dose levels evaluated in Part A.

For Part B, dose escalation decisions will be based on data obtained from 6 or more subjects receiving GSK2982772 at the prior dose level. The review of the data set will consist at a minimum of: listings of all AEs, clinical laboratory results, flagged vital signs, flagged findings during continuous cardiac monitoring (telemetry) and ECG findings through Day 16 of the previous cohorts(s) in Part B. Also included will be any PK results derived through at least Day 7 of the previous cohort(s).

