5. CONSIDERATIONS FOR DATA ANALYSES AND DATA HANDLING CONVENTIONS

5.1.	Study Treatment & Sub-grou	up Display Descriptors

Treatment Group Descriptions											
	RandAll NG	Data Displays for Reporting									
Code	Description	Description	Order in TLF								
Р	Placebo TID Single Dose	Placebo	1								
Q	Placebo BID Single Dose	Placebo	1								
Α	GSK2982772 120 mg TID Single Dose	GSK 120 mg TID	2								
В	GSK2982772 240 mg TID Single Dose	GSK 240 mg TID	3								
С	GSK2982772 360 mg BID Single Dose	GSK 360 mg BID	4								
R	Placebo TID Repeat Dose	Placebo	1								
S	Placebo BID Repeat Dose	Placebo	1								
D	GSK2982772 120 mg TID Repeat Dose	GSK 120 mg TID	2								
E	GSK2982772 240 mg TID Repeat Dose	GSK 240 mg TID	3								
F	GSK2982772 360 mg BID Repeat Dose	GSK 360 mg BID	4								
G	GSK2982772 Cohort 3 Repeat Dose	GSK 120 mg TID	2								
н	GSK2982772 Cohort 4 Repeat Dose	GSK 240 mg TID	3								
J	GSK2982772 Cohort 5 Repeat Dose	GSK XX mg TID/BID ^[1]	3 or 4								
Т	Placebo Cohort 3 Repeat Dose	Placebo	1								
U	Placebo Cohort 4 Repeat Dose	Placebo	1								
V	Placebo Cohort 5 Repeat Dose	Placebo	1								

NOTES:

^[1] Dose level not required as the study met the PK stopping criteria at the end of Cohort 4.

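### After Day 1 of Part B, no 12-lead ECG, vital-sign set or neurological examination is scheduled near peak, so effects on these measures that build with duration of dosing and show at peak are not assessed

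*SAP*

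**What the plan says.** On Day 1 of Part B the SAP schedule (10.2.1.2) places ECGs and vital signs, timed from the first dose, at "40min, 2hr, 4hr, 7hr (pre- 2 nd dose), 9hr, 14hr (pre-3 rd dose), 16hr, 24hr, 48hr" for TID and "40 min, 2hr, 4hr, 12hr (pre- 2 nd dose), 14hr, 24hr, 48hr" for BID. With TID doses at 0, 7 and 14 h, the 2, 9 and 16 h readings are each 2 h after a dose. With BID doses at 0 and 12 h, the same holds for 2 and 14 h. The 24 and 48 h readings fall at the next two mornings' pre-dose times.

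From there the note reads "On Days 3 to 14, pre-dose" samples only. The last timed readings are 24 and 48 h after the first and last doses of Day 14. The pre-dose sentence follows the BID text, but no post-dose time is listed for TID on those days either.

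Neurological examinations are at 2, 9 and 16 h (TID) or 2 and 14 h (BID) on Day 1, then at 24 and 48 h. After that: "To be completed pre-dose on Day 7 and then 48hr" after the last Day 14 dose.

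On pharmacokinetics, Protocol 5.7 places Cmax "at approximately 2 hours post-dose, GSK2982772 concentrations decline rapidly until about 12 hours post-dose", with a half-life of about 2-3 h. It expects steady state by Day 2, negligible accumulation, and similar Day 1 and Day 14 exposure margins.

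Protocol Section 2 states that assessment times "may be altered during the course of the study based on newly available data (e.g. to obtain data closer to the time of peak plasma" levels), documented in a Note to File without an amendment.

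**The concern.** The primary objective is the safety and tolerability of repeat doses, and vital signs and 12-lead ECG are listed primary endpoints (Protocol Section 4). Fourteen days of dosing can show what one day cannot: effects that take time to develop. For a drug with a short half-life, such an effect may be visible only near peak. After Day 1 these three measures are taken only at trough or after washout.

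This bears on risks that the protocol names. Section 3.3.1 lists CNS effects and, from a single-dose monkey study, reduced respiratory rate and minute volume. Amendment 02 reports cardiac arrhythmias in Cohorts 1 and 2 that led to a temporary dosing hold. The response added a screening Holter but no near-peak 12-lead ECG later in dosing. Post-dose PK profiles are drawn on Days 9, 11 and 14, the first two after standard and high-fat breakfasts, with no ECG or vital signs scheduled beside those peaks.

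**Working it through.** **Inputs.** Tmax 2 h and half-life 2-3 h (Protocol 5.7); doses at 0, 7, 14 h (TID) or 0, 12 h (BID) for 14 days (Protocol 5.1); assessment times from SAP 10.2.1.2. The one-compartment oral model is my assumption.

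**1. The protocol's own premise.** Fraction of steady state at 24 h = 1 - 2^(-24/t½):
- t½ = 2 h: 99.98%
- t½ = 2.5 h: 99.87%
- t½ = 3 h: 99.61%

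Steady state by Day 2 is reproduced. In the full model below, the Day 14 to Day 1 ratio of the highest daily Cmax is 1.000-1.005, and of AUC(0-24) 1.02-1.06 (TID) or 1.02-1.05 (BID). Cmax after the first dose of the day is 7-17% (TID) or 3-9% (BID) higher on Day 14.

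**2. Simple decay check.** Fraction of peak remaining pre-dose = 0.5^((gap - 2)/t½), where the gap since the last dose is 10 h (TID) or 12 h (BID):
- TID: 0.5^(8/2) = 6% to 0.5^(8/3) = 16%
- BID: 0.5^(10/2) = 3% to 0.5^(10/3) = 10%

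This omits absorption and residue from earlier doses, so it is slightly low.

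**3. Superposition.** C(t) = sum over doses d of ka/(ka - ke) × [exp(-ke(t - d)) - exp(-ka(t - d))], with ke = ln 2/t½ and ka solved so that Tmax = 2 h (ka = 0.69, 0.82 and 0.92 for t½ = 2, 2.5 and 3 h).

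Worked case, TID, t½ = 2 h. Here ka = 2ke, so each dose contributes 2 × (2^(-g/2) - 2^(-g)) at a gap of g hours.
- At 24 h, gaps 10, 17 and 24 h: 0.0605 + 0.0055 + 0.0005 = 0.0665
- At 16 h, gaps 2, 9 and 16 h: 0.5000 + 0.0845 + 0.0078 = 0.5923
- Ratio 0.0665/0.5923 = 11.2%. The 16 h value is 99.3% of the Day 14 Cmax, so the trough is about 11% of Cmax.

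All cases, as % of Day 14 Cmax over t½ = 2-3 h:

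| Scheduled time | TID | BID |
|---|---|---|
| Day 1, 2 h | 75-84 | 92-97 |
| Day 1, 9 h | 95-98 | - |
| Day 1, 16 h (TID) or 14 h (BID) | 99 | 99-100 |
| Pre-dose Days 2-14, and 24 h after first Day 14 dose | 11-20 | 6-13 |
| 48 h after first Day 14 dose | <0.1 | <0.1 |
| 24 h after last dose | 0.1-0.8 | 0.1-0.8 |
| 48 h after last dose | about 0 | about 0 |

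**4. Count.** A TID course has 14 × 3 = 42 doses. Doses 1-3 have near-peak readings on these measures; doses 4-42 have none scheduled.

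**5. ECG row against its own note.** The note asks for an ECG 48 h after the first dose, which is Day 3, and 24 and 48 h after the Day 14 doses, which run into Days 15 and 16. The row appears to mark Day 4 but not Days 3, 15 or 16. Protocol 10.5 has the Dose Escalation Committee review "ECG findings through Day 16 of the previous cohorts(s) in Part B". Amendment 01 moved the Part B neurological examination from Day 4 to Day 3 because 48 h falls on Day 3; the ECG row still shows Day 4. Column marks can shift in a text copy of this table, and the nearby telemetry row is misaligned, so this needs checking on the laid-out page.

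**The case against.** The strongest reply is that steady-state peak is measured. On the protocol's predicted PK, the 16 h (TID) and 14 h (BID) readings on Day 1 are at about 99% of the Day 14 peak, with ECG, vital signs and neurological examination all taken. That stands for any effect driven by concentration alone. It does not reach effects that depend on how long the subject has been dosed.

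A reader might infer that the primary safety endpoint is never observed near peak after Day 1. The documents do not support that. Adverse events are a primary endpoint reviewed every day, and physical examinations carry no pre-dose restriction. Neurological examination is not itself a listed primary endpoint, and the risk table's CNS monitoring is through adverse events.

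A reader might also infer from the SAP's note that "the study met the PK stopping criteria at the end of Cohort 4" that the drug accumulated, so that Day 1 does not represent Day 14. That does not follow. The criterion in Protocol 8.1.2 compares the 95th percentile of predicted AUC and Cmax with monkey values at the NOAEL, so it concerns absolute exposure. High exposure without accumulation can meet it.

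Nor are all the QTc displays reassuring by construction. SAP Tables 2.37 and 2.39 report maximum post-baseline QTc and maximum increase, which include the Day 1 near-peak ECGs. The limitation falls on by-visit change tables such as 2.38 and 2.40.

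On food, the earlier 40 mg result showed similar rate and extent of absorption with a time lag (Protocol 5.6), so fed dosing alone is a weak argument.

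Telemetry has a second block around Day 14 and goes to the Dose Escalation Committee. It covers rhythm and rate, but not 12-lead intervals, blood pressure, respiratory rate or neurological status, and the SAP lists no display for it.

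**Conclusion.** The gap is real and narrow. After Day 1 of Part B, every timed 12-lead ECG, vital-sign set and neurological examination is at about 11-20% (TID) or 6-13% (BID) of peak, or under 1% from 24 h after the last dose. Effects on these measures that depend on duration of dosing and show at peak are not assessed. Only daily adverse-event collection, untimed physical examinations and Day 14 telemetry can cover that time.

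The percentages assume one-compartment kinetics and that a Tmax of 2 h and half-life of 2-3 h hold at the doses studied; the linear PK behind them is documented only up to 120 mg BID. The schedule finding itself needs no model. This is an inexpensive improvement to the design, not a reason to set aside the safety results. The apparent mismatch in the ECG row is a separate, minor point and is less certain until checked on the page.

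**What to change.** In the Part B schedule, move the existing Day 14 ECG and vital signs, and the existing Day 7 ECG, vital signs and neurological examination, from pre-dose to 2 h after the first dose. On Day 14 the 2 h PK and metabolite samples are already drawn, so ECG and vital signs would sit beside a measured concentration. On Day 7 only a pre-dose PK sample is planned, so that reading would be unpaired.

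No procedure is added, participants are resident, and Protocol Section 2 allows the change by Note to File. The cost is the trough reading on those two days; trough readings on other days remain. If no Part B dosing remains, as the SAP's Cohort 5 note suggests, the change can only serve later repeat-dose work on this schedule. In that case the study report should state that by-visit ECG and vital-sign summaries after Day 1 are trough or washout values.

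Separately, check the ECG row for Days 3, 4, 15 and 16 on the laid-out table, and reconcile it with its own note and with the committee's review through Day 16.
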